4.2.1.3 Freedom from RA lead-related complications in the chronic time period

4.2.1.4 Freedom from RV lead-related complications in the chronic time period

The lead safety endpoint will be assessed separately for the RA and RV leads for the chronic (2 months through the 12 month visit) time period.

The hypothesis is formally expressed as:

H₀: Freedom from lead related complications from the 2 month through the 12 month visit \leq 95%

H_a: Freedom from lead related complications from the 2 month through the 12 month visit $>$ 95%

The objective performance criterion of 95% used for this objective denotes the minimum level of adequate safety for the RA or RV leads in the chronic time period. This endpoint will be tested separately for the RA and the RV leads. Only those complications occurring by the 12 month visit and adjudicated by the Clinical Events Committee as RA lead or RV lead complications will be used in the estimation of these endpoints.

Sample Size

Simulation was used to calculate the sample size requirements for testing the Kaplan-Meier estimated survival probability for the freedom-from-complication endpoint. The SCORE Registry, containing patients who were implanted with an RA and RV market approved Tendril™ family of leads, was used to estimate freedom from lead related complications in the chronic time period. Using these estimates derived from the SCORE registry data, the expected proportion of patients free from RA lead related complications from 2 months post-implant through 12 months is 0.996 with a 95% lower confidence bound of 0.994. Similarly, for the RV lead, the expected proportion of patients free from RV lead related complications from 2 months post-implant through 12 months is 0.998 with 95% lower confidence bound of 0.997. Taking a conservative expected complication free rate of 0.98, with a study size of 800 RV leads and 400 RA leads patients and a Type 1 error rate for the chronic time

period hypothesis test of $\alpha = 0.025$ for a one-sided test, the power is greater than 98% for the RV leads and greater than 85% for the RA leads.

Patient Group

All patients who have had an attempted implant or a successful implant of an Accent MRI system will be included in this endpoint.

Patients who are lost to follow-up or withdrawn prior to the 12 month follow-up visit due to an RA or RV lead related complication will be analyzed as having experienced a complication at the date of the complication. Patients who withdraw for reasons unrelated to an RA or RV lead related complication will be censored at the date of withdrawal.

Analysis

The desired outcome is to reject both null hypotheses for the RA and RV endpoints. The RA and RV hypothesis will be tested separately. The null hypothesis for the RA or RV endpoints will be rejected at the 2.5% significance level if the 95% lower limit of a two-sided confidence interval for the freedom from RA or RV lead-related complications between 2 months and 12 months is greater than 95%. The confidence interval will be constructed using the log-log transformation of the event free estimate at 12 months.

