Patients who are lost to follow-up or withdrawn prior to the 2 month follow-up visit due to an RA or RV lead related complication will be analyzed as having experienced a complication at the date the complication occurred. Patients who withdraw for reasons unrelated to an RA or RV lead related complication will be censored at the date of withdrawal.

Analysis

The desired outcome is to reject both null hypotheses for the RA and RV endpoints. The RA and RV hypothesis will be tested separately. The null hypothesis for the RA or RV endpoints will be rejected at the 2.5% significance level if the 95% lower limit of a two-sided confidence interval for the freedom from RA or RV lead-related complications by 2 months is greater than 92%. The confidence

interval will be constructed using the log-log transformation of the event free estimate at 2 months.

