4.2.4.1 Freedom from system-related complications

The hypothesis is formally expressed as:

H_0 : Freedom from system related complications through the 12 month visit $\leq 80\%$

H_a : Freedom from system related complications through the 12 month visit $> 80\%$

The desired outcome is to reject the null hypotheses. The null hypothesis will be rejected at the 5% significance level if the 95% lower confidence limit for the freedom from system related complications at 12 months is greater than 85%.

Simulation was used to calculate the sample size requirements for testing the Kaplan-Meier estimated survival probability for the freedom-from-complication endpoint. The expected proportion of patients free from system related complications at 12 months is 0.975 (95% CI: 0.924, 0.992) using data from the VICTORY pulse generator IDE study (G050191). For a study size of 800 patients and a Type 1 error rate for the hypothesis test of $\alpha = 0.05$ for a one-sided test, the power is greater than 98%.

Patient Group

All patients that have had an attempted implant or a successful implant of an Accent MRI system will be included in this endpoint.

Patients who are lost to follow-up or withdrawn prior to the 12 month follow-up visit due to a system related complication will be analyzed as having experienced a complication at the date of withdrawal. Patients who withdraw for reasons unrelated to a system related complication will be censored at the date of withdrawal.

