9.0 Withdrawals

Withdrawal is defined as termination of participation of a patient from a clinical trial. All reasonable efforts should be made to retain the patient in the clinical trial until completion of the clinical trial. Reasons for withdrawal include, but are not limited to the following:

- Patient Death
- Patient and/or Family Request
- Patient Lost to Follow-Up: Patient will be considered “lost to follow-up” after a minimum of 2 documented phone calls by personnel at the investigational center to the patient or emergency contact and a certified letter is sent to the last known address
- Patient Participation terminated by Investigator
- Sponsor Request
- Unsuccessful Implant
- If a system explant occurs without replacement of an Accent MRI™ system and an MRI scan has not been performed after implant.

A WITHDRAWAL Case Report Form should be completed and sent to St. Jude Medical CRMD, Sylmar, CA.

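### Lead-safety Kaplan-Meier analyses censor at a withdrawal date that is undefined for patients lost to follow-up; read literally, unobserved time counts as complication-free and the false-pass rate can exceed 2.5%

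*Combined protocol and SAP*

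**What the plan says.** The acute (4.2.1.1, 4.2.1.2) and chronic (4.2.1.3, 4.2.1.4) lead-safety endpoints share one censoring sentence under Patient Group: "Patients who withdraw for reasons unrelated to an RA or RV lead related complication will be censored at the date of withdrawal". A patient who leaves because of a lead complication is counted as an event on the date of the complication.

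Section 9.0 supplies the definition: "Withdrawal is defined as termination of participation of a patient from a clinical trial". It lists loss to follow-up among the reasons, and that status applies "after a minimum of 2 documented phone calls by personnel at the investigational center to the patient or emergency contact and a certified letter" has been sent. No section says which date is then recorded as the withdrawal date, and last contact is not mentioned.

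The secondary endpoint in 4.2.4.1 censors in the same way, but dates events differently: a patient withdrawn because of a system complication "will be analyzed as having experienced a complication at the date of withdrawal".

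Missing-data analyses are planned for MRI safety (4.2.2), MRI efficacy (4.2.3) and the secondary endpoints (4.2.4.4). None is planned for 4.2.1.

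**The concern.** Kaplan-Meier censoring should stop the clock when the patient's status was last known. If a lost patient stays in the risk set until the site has finished its calls and letter, the denominator includes person-time in which a complication treated elsewhere could not have been seen. The estimated hazard is then too low and freedom from complications too high. The error always runs towards rejecting the null, on four endpoints that each claim a one-sided 2.5% level, and no planned sensitivity analysis would show it.

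**Working it through.** **Inputs from the plan (4.2.1).** Chronic: criterion 95%, planning rate 0.98. Acute: criterion 92%, planning rate 0.97. 400 RA and 800 RV leads; one-sided alpha 0.025; log-log lower limit. Visit windows from Table 3: 2 months ±7 days, 6 and 12 months ±60 days. **Assumptions, not in the documents:** the loss rate, and the gap from last contact to withdrawal.

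**Step 1: reproduce the stated power.** With no censoring and d events in n leads, S = 1 − d/n, σ = √[d/(n(n−d))], and the lower limit is exp{−|ln S| · exp(1.96σ/|ln S|)}. For chronic RA with d = 11: S = 0.9725, |ln S| = 0.02789, σ = √[11/(400×389)] = 0.00841, so the limit is exp(−0.02789 × 1.806) = 0.9509, a pass. With d = 12 it is 0.9478, a fail. Power and false-pass rate are binomial tails at that cut-off.

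| Endpoint | Max events to pass | Power | False-pass rate at the criterion |
|---|---|---|---|
| Chronic RA | 11 | 89.0% | 1.90% |
| Chronic RV | 27 | 99.6% | 1.71% |
| Acute RA | 21 | 99.5% | 2.17% |
| Acute RV | 48 | >99.9% | 1.86% |

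All the stated power bounds hold (chronic above 98% RV and above 85% RA; acute above 98%). The test starts below 2.5%.

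**Step 2: how long the gap could be.** A patient last seen at month 2 is not overdue until the 6-month window closes, near month 8: a gap of about 6 months. One last seen at month 6 is not overdue until about month 14, past the 12-month estimate.

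**Step 3: the bias by hand.** Let 10% be lost, half last seen at month 2 and half at month 6, withdrawn when the next window closes. True chronic freedom is 95%, so the monthly hazard is h = −ln(0.95)/10 = 0.005129. The observed share of the nominal risk set is 0.95 in months 2–6, 0.90 in months 6–8, and 0.90/0.95 in months 8–12. The estimated cumulative hazard is h × (4×0.95 + 2×0.90 + 4×0.90/0.95) = 0.005129 × 9.389 = 0.04816, so the estimate is exp(−0.04816) = 0.953 instead of 0.950.

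**Step 4: false-pass rate, chronic, by simulation.** True freedom is 95% and events after last contact are unobserved. There were 20,000 runs per cell for constant gaps and 40,000 for visit-driven gaps; Monte Carlo standard error is about 0.1 point. Entries are RA / RV under literal withdrawal-date censoring.

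| Loss | 1-month gap | 3-month gap | 6-month gap | Visit-driven gap |
|---|---|---|---|---|
| 2% | – | – | – | 2.3% / 2.2% |
| 5% | 1.8% / 2.2% | 2.3% / 2.3% | 2.6% / 2.3% | 2.6% / 2.9% |
| 10% | 1.7% / 2.3% | 2.0% / 2.9% | 3.1% / 3.7% | 3.1% / 4.7% |
| 20% | 1.8% / 2.5% | 2.7% / 4.3% | 4.3% / 6.9% | 5.2% / 9.9% |

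A repeat of the visit-driven case gave 2.3% / 2.4%, 2.7% / 2.9% and 3.0% / 5.0% at 2, 5 and 10% loss. Censoring at last contact gave about 1.4 to 2.4% throughout, with a mean estimate of 0.950.

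**Step 5: acute period** (true freedom 92%, gaps of 1 or 2 months, RA and RV together): 2.1–2.4% at 2% loss, 2.7–3.0% at 5%, 2.7–4.6% at 10%.

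**Step 6: at the planning rate.** With chronic freedom 0.98, 10% loss and a 3-month gap, moving from last-contact to withdrawal-date censoring changes the pass probability from 85.4% to 86.8% (RA) and from 99.6% to 99.7% (RV).

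**The case against.** The strongest reply is that the plan never chooses an administrative date over the last contact. It says only date of withdrawal, and section 9.0 fixes the effort required before a patient is considered lost, not the date entered. A site that recorded the last contact would comply. That stands: a reader might infer that the plan deliberately credits unobserved time, and the text does not go that far. But nothing directs sites to the last contact, and the literal reading points to a later date.

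Second, two calls and a letter need not take six months, and with short gaps the level holds. This also stands, with one qualification: visits are 4 and 6 months apart with ±60-day windows, so a missed visit may not be noticed quickly.

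Third, the rule matters only for lost patients. For a death or a refusal known on its date, the withdrawal date is already the last contact.

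Fourth, overall success requires every primary endpoint to pass, so a raised rate on one endpoint is not the same increase for the trial. That is correct; the figures above are per endpoint.

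On 4.2.4.1, a reader might infer that late complications routinely drop out of the 12-month estimate, because section 4.4.4 withdraws patients explanted without replacement after 30 days. But the rule covers only patients withdrawn before the 12-month visit, so an event moves past month 12 only when that visit falls late in its +60-day window. The inconsistency with the primaries is real but minor.

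**Conclusion.** The point holds in conditional form. On a literal reading, the four lead-safety primaries count time after last contact as complication-free for lost patients, and the bias is always towards passing: about 0.05 to 0.6 percentage points in the chronic scenarios in the working.

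It would be tempting to say that the 2.5% level is broken. The documents do not support that, because they give neither the loss rate nor the contact-to-withdrawal gap. In the chronic period the level is exceeded from roughly 5% loss if gaps follow the visit schedule, or from about 10% with constant gaps of several months (RV first). It is kept at about 2% loss, and with 1-month gaps up to 20% loss. If true performance is near the planning rate, the conclusion is hardly affected; what is at stake is error control for a lead whose true performance is close to the criterion. Since the better rule costs almost nothing, it should be written in.

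**What to change.** - In 4.2.1.1 to 4.2.1.4 and 4.2.4.1, replace censoring at withdrawal with censoring at the last date on which lead or system status was ascertained: visit, interrogation, documented contact or death.
- In 4.2.4.1, date the event at the complication, as the primaries do.
- Extend the tipping-point analysis of 4.2.4.4 to the four lead-safety primaries, turning patients censored before the 2- or 12-month estimate into failures one at a time.

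This changes analysis wording and adds no visits. It costs a slightly lower estimate, a slightly wider interval and a little more analysis work. The documents list the forms but not their fields, so confirm first that the last-contact date can be derived from the visit forms.

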4.2.2 Primary MRI Safety Endpoint: Freedom from MRI Scan-Related complications

An MRI Scan-Related complication is a complication caused by the interaction between the investigational pacing system and the MRI system that occurs during the MRI scan, including the time the patient is within the 5 Gauss line of the MRI system, up through the patient's 1 month post MRI visit. In addition, complications occurring due to the patient's MRI programming will be considered MRI scan related by the Clinical Events Committee (CEC).

The hypothesis is formally expressed as:

H_0 : Proportion of patients who are free from MRI scan-related complications between the MRI scan and one month post MRI visit $\leq 90\%$

H_a : Proportion of patients who are free from MRI-scan related complications between the MRI scan and one month post MRI visit $> 90\%$

The comparison criterion of 90% used for this objective denotes the minimum level for adequate safety following the MRI scan. Complications that can be attributed to the MRI scan are expected to occur within one month of the scan.¹⁹ Therefore, assessing this objective one month post-MRI scan will capture all MRI scan-related complications following the MRI scan procedure.

Sample Size

The expected proportion of patients free from complications under the null hypothesis is 0.90, and the Type 1 error rate is set at $\alpha = 0.025$ for the one-sided test. Assuming the portion of patients free from complications of 0.97, a sample size of 133 MRI patients provides a power level of 90% for this endpoint.

In another manufacturer's study involving an MRI conditional pacemaker, the complication free rate as observed to be 100%.¹⁹ Therefore, an assumption of 97% complications-free rate is assumed in the sample size calculation.

The objective will be evaluated using a one-sided z-test with variance of the test statistic based on the hypothesized value of 0.90 for the binomial proportion. The desired outcome is to reject the null hypothesis.

Patient Group

All patients implanted with the Accent MRI system who undergo an MRI scan and have completed their 1 month post MRI visit, or have an MRI-related complication before the end of the 1 month post MRI visit date will be included in the analysis of this endpoint.

Analysis

The analysis will be conducted on the per-protocol (PP) population. The per-protocol population includes patients who meet the following criteria:

- Successfully implanted with the Accent MRI system
- Have MRI visit data
- Meet the MRI Conditions of Use
- Received an MRI scan
- Have 1-month post MRI visit data

All individual primary safety endpoints must be successful (reject the null hypothesis at the $\alpha = 2.5\%$ level) for the safety endpoint to be successful.

A supporting analysis will also be performed using all patients who undergo an MRI scan. For this analysis, each missing data point will be replaced by a failure one at a time. Each time a new failure is added the analysis will be re-run. This continues until either all missing data has been replaced with a failure or the test becomes non-significant (i.e. the interpretation of the results changes). The proportion of missing data that would need to be a failure in order to change the analysis results will be reported and discussed.

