4.2.3 Primary MRI Efficacy Endpoints

4.2.3.1 Proportion of patients free of atrial capture threshold increase of > 0.5V at 0.5ms from before and to one month after the MRI scan

4.2.3.2 Proportion of patients free of ventricular capture threshold increase of > 0.5V at 0.5ms from before to one-month after the MRI scan

The hypothesis is formally expressed as:

H_0 : Proportion of patients with threshold increase of $\leq 0.5V$ at 0.5ms from before to one month post MRI visit $\leq 90\%$

H_a : Proportion of patients with a threshold increase of $\leq 0.5V$ at 0.5ms from before to one month post MRI visit $> 90\%$

The desired outcome is to reject the null hypothesis. The null hypothesis is rejected at 2.5% significance level if the lower bound of the two-sided 95% confidence bound on the proportion of patients with a threshold increase of $\leq 0.5V$ at 0.5ms from before to one month post MRI visit is greater than 90%.

Sample Size

A success (Post-MRI scan Threshold – Pre-MRI scan Threshold) is defined as a patient who experiences an increase in threshold less than or equal to 0.5 volts at the 1 month post-MRI visit compared to their pre-MRI testing (MRI visit). In this case post MRI capture Threshold \leq pre MRI capture Threshold + 0.5 volts.

The % of Success (Post-MRI scan Threshold – Pre-MRI scan Threshold) is defined as the number of patients with successes divided by the analyzable patients.

In another manufacturer's study involving an MRI conditional pacemaker, the proportion of patients with an increase in threshold less than or equal to 0.5 volts at the 1 month post-MRI visit compared to their pre-MRI testing was 100%.¹⁹ Therefore, an assumption of 98% of successes (Post MRI scan-Pre-MRI scan threshold) in the atrium and ventricle is assumed in the sample size calculation.

A sample size of 93 patients provides 90% power to demonstrate a success rate greater than 90% for the atrial and ventricular endpoints, respectively, at the 2.5% significance level.

Analysis

The analysis will be conducted on the per-protocol population. The per-protocol population includes patients who meet the following criteria:

- Successfully implanted with the Accent MRI system
- Have MRI visit data
- Meet the MRI Conditions of Use
- Received an MRI scan
- Have 1 month post MRI visit data

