4.2.7 Definitions to be used in the MRI study

Abnormal Lead Pacing Impedance: Measured pacing impedances with values $\leq 200 \Omega$ or $\geq 2000 \Omega$

Adverse Event: Any unfavorable clinical event which impacts, or has the potential to impact the health or safety of a patient caused by or associated with a study device or intervention. Adverse events are classified as complications or observations.

Complication: An adverse event caused by or associated with the study device, system component(s), and or procedure that requires invasive intervention (e.g. lead dislodgment requiring repositioning).

Cardiac Tamponade: Confirmed or suspected accumulation of fluid in the pericardial space

Cardiac Perforation: An excursion of the lead through the cardiac muscle. Signs and symptoms of a perforation by an intra-cardiac lead

may include radiographic evidence of excursion of the lead into the pericardial sac, abnormal echocardiography indicative of a perforation, the accumulation of fluid in the pericardium, cardiac tamponade, or patient symptoms such as chest pain and discomfort

Diaphragmatic/Phrenic Nerve Stimulation: Electrical activation of the diaphragm muscle by the device output pulse. The abrupt diaphragmatic contraction is noted clinically as hiccups associated with each pacing stimulus. The pacing stimulus may stimulate the diaphragm either directly or indirectly via the phrenic nerve.

Elevated Pacing Thresholds: Pacing thresholds > 2.0 V at 0.5 ms at implant. Following lead maturation at 6-8 weeks, an increase in pacing thresholds of 1.2 V at 0.5 ms or greater between visits. This definition is intended to serve as a guideline and it is understood that individual patients may have unique situations

Lead Dislodgement: The movement of a pacing lead from its originally implanted position resulting in elevated pacing thresholds or a decrease in sensing

Lead Fracture: A break in a conduction coil of a pacing or defibrillation lead typically evidenced by an increase in impedance, intermittent or complete loss of capture, intermittent or complete loss of sensing, noise on the intra-cardiac electrogram and visual signs of conductor coil fracture on x-ray

Lead Insulation Damage: A disruption to the integrity of the lead insulation without disruption of the conductor coil. An insulation break may be indicated by a drop in impedance, and can cause loss of capture or sensing problems

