4.4.4 Complete System Explants

If the patient has the entire Accent MRI system removed at any time during the study, and the patient will not receive a replacement Accent MRI system, follow the patient for 30 days, and withdraw the patient from the study. Complete and submit the forms listed below to St. Jude Medical. A system revision form is not required to be submitted.

- Withdrawal Form
- Product Out of Service Form
- Adverse Event Form, if applicable
- Death Form, if applicable

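### Section 4.2.2 contradicts itself on whether a scanned patient with a known complication but no 1-month visit enters the primary MRI safety test

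*Combined protocol and SAP*

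**What the plan says.** All of this is in Section 4.2.2 of the combined protocol and SAP unless another section is named.

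- **Patient Group.** Implanted and scanned patients enter if they completed the 1-month visit, "or have an MRI-related complication before the end of the 1 month post MRI visit date will be included" in the analysis. The second route does not need the visit.
- **Analysis.** "The analysis will be conducted on the per-protocol (PP) population". Five criteria follow, and the last is "Have 1-month post MRI visit data". No alternative is given for a patient who has already had a complication.
- **Supporting analysis.** "A supporting analysis will also be performed using all patients who undergo an MRI scan", with missing outcomes turned into failures one at a time. It supports the primary test and does not replace it.
- **Decision rule.** Every primary safety endpoint must reject its null. Section 4.2.3 ends by making overall success depend on all primary safety and efficacy endpoints.

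The other complication endpoints state a rule for this kind of patient. Sections 4.2.1 (lead, acute and chronic) and 4.2.4.1 (system) count patients lost or withdrawn because of a relevant complication as having had the event.

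**The concern.** Take a scanned patient who has an adjudicated scan-related complication and then dies or withdraws before the 1-month visit. The outcome is already known: a failure. Patient Group keeps this patient and the list drops the patient. Both rules are worded as binding, and neither refers to the other. If the list governs, the second route in Patient Group has no effect on the primary test.

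The difference runs one way. On the visit criterion, a patient without a complication and without the visit is out under both rules, so only failures change status. The same data could therefore give two primary safety results, with the list's result never the less favourable. The choice between the rules should not be left until the data are in hand.

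**Working it through.** **Inputs from Section 4.2.2.** Null rate 0.90, planned rate 0.97, one-sided alpha 0.025 (critical value 1.960), z-test with variance at the null, stated n = 133 for 90% power.

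**Other sizes.** Section 4.1 caps the MRI phase at 363 patients. Section 4.2.3 states that atrial sensing needs 165 patients. Its per-protocol list repeats the same five criteria and adds more, so every patient analysable for atrial sensing also meets the safety list. If that endpoint reaches its stated size, the safety set has at least 165 patients. The figure of 133 is therefore a lower reference point.

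**The plan's own figure.** n = [(1.960·√(0.90·0.10) + 1.2816·√(0.97·0.03)) / 0.07]² = [(0.5880 + 0.2186) / 0.07]² = 132.8, rounded up to 133. The stated size reproduces.

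**At the boundary.** z = (observed rate − 0.90) / √(0.09/n).

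- 6 failures in 133: 127/133 = 0.9549, z = 2.11, pass.
- 7 failures in 133: 126/133 = 0.9474, z = 1.82, no pass.
- The same 7 with one dropped for want of the visit: 126/132 = 0.9545, z = 2.09, pass.
- At 363 the same happens with 26 failures: 337/363 gives z = 1.802 (no pass) and 337/362 gives z = 1.962 (pass).

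One such patient is enough, but only at the boundary.

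**How often that would happen.** The documents give no share d of complication patients who lack the visit, so d = 5%, 10% and 25% are assumed, with all other patients having it. At the planned rate 133 × 0.03 = 3.99 complications are expected, so 25% means about one of four, an extreme case. Failures F ~ Bin(n, 1 − p); dropped failures D ~ Bin(F, d), taken from numerator and denominator. A reversal is z(F, n) ≤ 1.960 with z(F − D, n − D) > 1.960. Exact enumeration gives, for d = 5% / 10% / 25%:

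| True rate | n = 133 | n = 165 | n = 363 |
|---|---|---|---|
| 97% (planned) | 1.9 / 3.7 / 7.5% | 1.4 / 2.6 / 4.9% | below 0.01% throughout |
| 95% (assumed) | 5.4 / 10.8 / 26.6% | 5.9 / 11.7 / 27.4% | 1.4 / 2.4 / 4.1% |

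Reversals from pass to no pass have probability zero in every case.

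**Error rate at the 90% null.** The chance of a false pass rises from 1.7% with none dropped to 2.6 / 4.0 / 11.9% at n = 133, and from 2.5% to 4.0 / 6.6 / 29.2% at n = 363. A larger sample removes the problem at the planned rate but does not protect the error rate at the null. There, 25% at n = 363 would mean about 9 of 36 complication patients without the visit (363 × 0.10 = 36.3; × 0.25 = 9.1), which no figure in the documents suggests.

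**The case against.** The strongest reply is that the text has a natural reading. Patient Group names exactly this patient and says the patient is included, and elsewhere in the plan the same heading carries the rule for withdrawals due to a complication. The five criteria match the first five of the capture-threshold list in Section 4.2.3, where "Have 1 month post MRI visit data" is indispensable because the endpoint is a measurement at that visit. The safety list may be carried-over text, with the inclusive rule intended. This is plausible, but no sentence says so, and the sentence that fixes the analysis set points to the list.

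The route is also narrow, and this stands. Section 4.2.7 defines a complication as "An adverse event caused by or associated with the study device, system component(s), and or procedure that requires invasive intervention", so a death without such an event is not a failure under either rule. Section 4.4.5.1 retains revised patients. For an explant without replacement, Section 4.4.4 says to "follow the patient for 30 days, and withdraw the patient from the study". What remains is mainly death or early withdrawal after a complication. The Clinical Events Committee adjudicates every adverse event and the supporting analysis covers all scanned patients, so a dropped failure would be visible. It would still not be counted in the test that decides the endpoint.

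A reader might infer that the other criteria conflict with Patient Group too, in particular "Meet the MRI Conditions of Use" and the requirement for MRI visit data. The documents do not support that. These are ordinary per-protocol restrictions, and no clause in Patient Group says that such patients must be kept regardless. A per-protocol set narrower than the Patient Group is not in itself a contradiction. The contradiction arises only where Patient Group expressly admits a patient whom the list excludes.

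**Conclusion.** Wrong as written (minor). The two rules in Section 4.2.2 contradict each other on the 1-month visit, and following the list can only favour success.

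The expected effect at the planning assumptions is small: a reversal chance of 1.4% to 4.9% at 165 patients and below 0.01% at 363. It becomes material only if the true rate is well below 97%, or if a sizeable share of complication patients miss the visit. Every probability rests on the assumed shares of 5% to 25%.

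A reader might go further and infer that the primary safety test is invalid, or that the plan intends to remove failures. Neither follows: the inclusive rule is in the plan, it may be the intended one, and the all-scanned analysis would show any such case.

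**What to change.** In the per-protocol list of Section 4.2.2, keep the last bullet, "Have 1-month post MRI visit data", and add to it:

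*, or had an MRI scan-related complication before the end of the 1-month post MRI visit date (counted as a failure)*

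Leave the other four bullets as they are. This carries the sponsor's own Patient Group rule into the list and should be done before the data are analysed.

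The cost is one clause. Adverse events are already reported and adjudicated, so no new data are needed, and the sample size of 133 does not change. The only downside is a possibly slightly less favourable observed rate.
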